After completion of treatment for 6 months (Week 25) and data collection for the principal analysis, the patients will continue on long-term avalglucosidase alfa treatment and follow-up for up to a total of 7 years in the study.

Cohort 3 patients receiving alglucosidase alfa during the treatment period (Day 1 to Week 25 [Month 6]) will have the option to switch to treatment with avalglucosidase alfa in the extension period or discontinue the study.

8.1.2 Extension period: Week 27 to Week 145 (Month 36) and additional extension period from Week 147 onwards

All patients (from Cohorts 1, 2 and 3) will receive avalglucosidase alfa administered by IV infusion qow starting at V16/W27 continuing up to V76/W145 for a total of up to 60 doses. In order to allow study participants to continue to receive the investigational medicinal product (IMP) after Week 145, the study is extended to an additional period of up to 226 weeks or until avalglucosidase alfa is approved in the patient's country, whichever comes first; (refer to Appendix C [[Section 17.3.1](#)] for definition applicable for UK patients) in which the patients will receive avalglucosidase alfa administered by IV infusion qow for up to an additional 72 doses.

- Participants in Cohort 1 will receive avalglucosidase alfa at a dose of 20 mg/kg qow. If a patient in Cohort 1, receiving 20 mg/kg qow avalglucosidase alfa, experiences further clinical decline at or after Week 25 when compared to prior to enrollment in ACT14132, and as defined by more rapid worsening of criteria of clinical decline, which is sustained on repeated study assessments, the patient may be managed per the discretion of the Investigator, which may include return to treatment with commercially available alglucosidase alfa (and termination of trial participation) or increasing the avalglucosidase alfa dose to 40 mg/kg qow (once this dose is considered acceptable after the end-of-cohort 2 DMC meeting) or MTD (once established) while being enrolled in the extension period of the study.
- Participants in Cohort 2 will receive avalglucosidase alfa at 40 mg/kg qow or MTD (once established).
- Participants in Cohort 3 will receive the MTD of avalglucosidase alfa as determined based on safety data from both dose levels in Cohort 1 and Cohort 2.

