9.1.1.7 Immunogenicity

Immunogenicity assessments will include the following:

- During the treatment period, pre-infusion samples from patients receiving avalglucosidase alfa will be collected at baseline and then every month for evaluation of anti-avalglucosidase alfa anti-drug antibody (ADA) and at baseline and every 3 months (V9 [Week 13], and V15 [Week 25]) for evaluation of anti-alglucosidase alfa ADA. In addition, samples will be collected at V3 (Day 8) to monitor for an early antibody response (for both anti-avalglucosidase alfa ADA and anti-alglucosidase alfa ADA). Pre-infusion samples from patients receiving alglucosidase alfa will be collected at baseline, V3 (Day 8), V9 (Week 13), and V15 (Week 25) for evaluation of anti-alglucosidase alfa ADA and at baseline and V15 (Week 25) for evaluation of anti-avalglucosidase alfa ADA.
- During the extension period, pre-infusion samples from patients receiving avalglucosidase alfa since the start of the study will be collected every 3 months for evaluation of

anti-avalglucosidase alfa ADA. Samples from patients in Cohort 3 switching to avalglucosidase alfa will be collected at V17 (Week 28), V18 (Week 29), and V20 (Week 33) to monitor for an early antibody response (for avalglucosidase alfa), followed by collection every month for 6 months and then every 3 months for evaluation of anti-avalglucosidase alfa ADA.

- ADA seropositive patient serum will be assessed for neutralizing antibodies to avalglucosidase alfa and/or alglucosidase alfa, as appropriate, including inhibition of enzyme activity and uptake.

Samples may be collected from patients and evaluated for IgE, complement activation, serum tryptase following moderate, severe, or recurrent mild IARs suggestive of hypersensitivity reactions ([Section 10.6](#)).

In the event a patient exhibits signs or symptoms suggestive of systemic immune-mediated reactions involving skin and other organs, serum samples are obtained for the evaluation of circulating immune complexes.

Leftover antibody samples will be stored for further analysis as needed.

See the study-specific laboratory manual as well as the study manual for guidelines on the collection and shipment of the samples.

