2.1 ANALYSIS ENDPOINTS

2.1.1 Demographic and baseline characteristics

The PAP baseline value is defined as the last non-missing value prior to first investigational medicinal product (IMP) intake, unless otherwise specified.

The ETP baseline value is defined as:

- The last non-missing value prior to first IMP intake in PAP for patients receiving avalglucosidase alfa from the beginning of this study;
- The last non-missing value prior to first IMP intake in ETP for patients switching to avalglucosidase alfa from alglucosidase alfa.

Demographic characteristics

Demographic variables are age at study entry (year), gender (Male, Female), race (American Indian or Alaska Native, Asian, Black or Africa American, Native Hawaiian or other Pacific Islander, White, Not Reported), ethnicity (Hispanic, non-Hispanic, Unknown, Not Reported).

Medical or surgical history

Medical or surgical history includes prior or existing condition in different body systems as well as prior or existing medical conditions/surgical procedures of specific interest.

Disease characteristics at baseline

Pompe disease history includes acid α -glucosidase (GAA) genotyping, CRIM (cross-reactive immunologic material) status, GAA enzyme activity, [REDACTED], [REDACTED], aspects of disability (Pompe medical history, ventilator and assistive mobility device use), age at first symptoms of Pompe disease, age at diagnosis of Pompe disease, age at first treatment with alglucosidase alfa, time from Pompe disease diagnosis to first infusion of study drug, time from first symptoms of Pompe disease to first infusion of study drug.

Pompe medical history includes:

- Cardiovascular history (evidence of cardiac involvement, current NYHA (the New York Heart Association) heart failure classification, congestive heart failure),
- Ears, nose, throat medical history (enlarged tongue, hearing loss),
- Gastrointestinal (hepatomegaly, gastroesophageal reflux),
- Respiratory history (pneumonia, tracheostomy, sleep disturbances, sleep apnea),
- Musculoskeletal history (muscle weakness in upper extremities, muscle weakness in lower extremities, scoliosis, joint contractures, and current ambulatory status, assisted walking device and wheelchair use).

Family history of Pompe disease history includes confirmed Pompe disease in other family members.

Retrospective Chart Review

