2.4.4 Analyses of safety data

In general, for PAP, the summary of safety results will be presented by study cohort and treatment arm. For the overall avalglucosidase alfa treatment period, the summary of safety results will be presented by initial planned dose levels among avalglucosidase alfa patients. For Cohort 3 alglucosidase alfa patients, the summary of safety results for ETP will be presented in separate tables.

In the PAP analysis, the safety analyses will be carried out with patients by the actual treatment received, irrespective of the treatment the patient has been randomized to. The actual treatment received is defined as:

- avalglucosidase alfa if the patient receives at least one infusion with this drug in PAP;
- alglucosidase alfa if the patient only receives alglucosidase alfa in PAP.

In the ETP analysis and/or overall evaluation of avalglucosidase alfa safety, the safety analyses will be carried out by the following 3 groups:

- AVAL/AVAL in ETP includes data in ETP among patients who received avalglucosidase alfa in PAP and ETP;
- ALGLU/AVAL in ETP includes data in ETP among patients who received alglucosidase alfa in PAP and received avalglucosidase alfa in ETP;
- AVAL/AVAL and ALGLU/AVAL in overall avalglucosidase alfa treatment period includes data in PAP and/or ETP among patients who received avalglucosidase alfa in that period.

General rules

All safety analyses will be performed on the safety population as defined in [Section 2.3.1](#), unless otherwise specified, using the following common rules:

- The safety baseline value is defined the same as the baseline definition in [Section 2.1.1](#).
- The potentially clinically significant abnormality (PCSA) values are defined as abnormal values considered medically important by the Sponsor according to predefined criteria/thresholds based on literature review and defined by the Sponsor for clinical laboratory tests, vital signs, and ECG (PCSA version dated January 2014 [[Appendix B](#)]).
 - PCSA criteria will determine which patients had at least 1 PCSA during the treatment epoch (for PAP and ETP respectively), taking into account all evaluations performed during this period, including nonscheduled or repeated evaluations.
 - The number of all such patients will be the numerator for the on-treatment PCSA percentage; the denominator will be the number of patients assessed for that given parameter in the treatment epoch by treatment group on the safety population.

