2.4.4.7 Analyses of immunogenicity parameters

Percentage of patients who seroconverted to avalglucosidase alfa and time to seroconversion will be summarized using summary statistics, by study cohort and treatment group, as well as by dose levels among avalglucosidase alfa treated patients for the overall avalglucosidase alfa treatment period.

Anti-avalglucosidase alfa and anti-alglucosidase alfa antibody titer values will be summarized using summary statistics at each study visit by study cohort and treatment group, as well as by dose levels among avalglucosidase alfa treated patients for the overall avalglucosidase alfa treatment period. Median and quartiles Q1 and Q3 titer values will be reported. All data will be presented in listings for each patient.

By patient listings will also display results of NAb, as well as results testing for IARs if clinically indicated (i.e., circulating immune complex, anti-avalglucosidase alfa IgE antibody, serum tryptase activity, complement activation, and skin testing). Descriptive summaries may also be provided as appropriate.

The following incidence rates will be summarized descriptively for each treatment group:

- ADA prevalence rate, defined as
$$100 \times (\text{number of patients with treatment-induced ADA} + \text{pre-existing ADA}) / (\text{number of evaluable patients})$$
- ADA incidence rate, defined as
$$100 \times (\text{number of patients with treatment-boosted + treatment-induced ADA}) / (\text{number of evaluable patients});$$
- Treatment induced ADA incidence rate, defined as,
$$100 \times (\text{number of patients with treatment induced ADA}) / (\text{number of evaluable patients with ADA negative at baseline});$$
- Treatment boosted ADA incidence rate, defined as
$$100 \times (\text{number of patients with treatment boosted ADA}) / (\text{number of evaluable patients with ADA positive at baseline});$$
- Incidence rate of NAbs (for inhibition of uptake, inhibition of activity and both, respectively), defined as
$$100 \times (\text{number of patients positive for NAbs}) / (\text{number of evaluable patients})$$

The kinetics of the immune responses will be analyzed as follow:

- Onset time of ADA will be analyzed descriptively using summary statistics including median and quartiles Q1 and Q3.
- Duration of ADA will be analyzed descriptively using summary statistics including median and quartiles Q1 and Q3. It will only be calculated for the patients with at least two ADA positive samples.

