2.5.3 Study day calculation

Based on study protocol, study Day 1 is the date of first study infusion (i.e., Week1 Day 1).

Study day for a given assessment is defined as the assessment date - date of first study infusion + 1 if the assessment date is on or after Day 1, or assessment date - date of first study infusion if the assessment date is before Day 1.

For cohort 3 patients, if a randomized patient is not treated (first infusion date is missing), study Day 1 is the date of randomization.

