2.5.4 Windows for time points

The visit windows for efficacy endpoints are defined in the following table. For analysis purpose, a larger window (as shown in the last column of [Table 5](#)) will be used. This will be applicable for those analyses requiring visit information.

The analysis visit will be defined by comparing the actual visit date with the nominal (or target) date and the corresponding analysis window from [Table 5](#). If more than one non-missing value is assigned to the same visit, then the one closest to the target date will be used in the by-visit analysis. Multiple values on the same date will be averaged first. If two assessments are on different dates but equal distance from the target date, the later date will be used.

For the safety analyses (laboratory, ECG and vital signs), the nominal visit will be used for the by-visit type of analyses.

Table 5 - Study visit nominal visit days and windows for efficacy endpoints

Scheduled Visit	Visit window defined in protocol in study days	Visit window for analysis purpose in study days
Screening/Baseline	Day -14 to -1	-28 to -1 (or 1 if before 1st infusion)
Week 13	Day 85 ±14	Day 0 (or Day 2 if Screening/baseline on Day 1) to 85 + 41
Week 25	Day 169 ±14	Day 169- 42 to 169 + 41 and prior to any ETP treatment
Week 37	Day 253 ±14	Day 253- 42 to 253 + 41 and after the 1st ETP treatment
Week 49	Day 337 ±14	Day 337- 42 to 337 + 41
Week 61	Day 421 ±14	Day 421 - 42 to 421 + 41
Week 73	Day 505 ±14	Day 505 - 42 to 505 + 83
Week 97	Day 673 ±14	Day 673- 84 to 673 + 83
Week 121	Day 841 ±14	Day 841- 84 to 841 + 83
Week 145	Day 1009 ±14	Day 1009- 84 to 1009 + 83 ±84

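### Overall-period laboratory tables by visit combine Cohort 3 switchers with Day 1 starters who are 26 weeks ahead of them in avalglucosidase alfa exposure

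*SAP*

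**What the plan says.** **Time scales.** SAP 2.5.3 gives one study-day rule: "Study day for a given assessment is defined as the assessment date - date of first study infusion + 1" (for assessments on or after Day 1). For a Cohort 3 control patient, that first infusion is alglucosidase alfa. SAP 2.5.4 then sets the visit label for by-visit safety tables: "For the safety analyses (laboratory, ECG and vital signs), the nominal visit will be used for the by-visit type of analyses". Neither section makes an exception for the overall avalglucosidase alfa period.

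**Pooling.** One of the three groups in SAP 2.4.4 is defined so: "AVAL/AVAL and ALGLU/AVAL in overall avalglucosidase alfa treatment period includes data in PAP and/or ETP among patients who received avalglucosidase alfa in that period". The same section also promises separate tables for the switchers' ETP safety results.

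**Tables by visit.** SAP 2.4.4.3 (laboratory) plans observed values and changes from baseline for each visit. SAP 2.4.4.7 (immunogenicity) plans antibody titres at each study visit. Both add the same extra presentation: "as well as by dose levels among avalglucosidase alfa treated patients for the overall avalglucosidase alfa treatment period". SAP 2.4.4.7 also plans graphs of titre over time for PAP, ETP and the overall period.

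**Start of drug.** Extension dosing is "qow starting at V16/W27 continuing up to V76/W145 for a total of up to 60 doses" (Protocol 8.1.2). Week 27 is therefore the switchers' first avalglucosidase alfa dose.

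**Baseline.** SAP 2.1.1 resets the ETP baseline of switchers to: "The last non-missing value prior to first IMP intake in ETP for patients switching to avalglucosidase alfa from alglucosidase alfa".

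**The concern.** A by-visit table for a drug-exposure period is read as a time course on that drug. Here the period and the switchers' baseline are tied to avalglucosidase alfa, but the row label is tied to the first study infusion of either drug. A single row then averages patients at quite different times on the drug.

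Safety is the primary endpoint, and the first months on avalglucosidase alfa matter most for early laboratory change and antibody response. In a pooled by-dose table, the switchers' first months would appear as mid-extension data, beside patients who have already been treated for half a year or more. Part of any movement from row to row would then reflect this mixture and not a change within patients.

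**Working it through.** **Step 1: check the nominal scale.** With target day = (week − 1) × 7 + 1, Week 25 gives 24 × 7 + 1 = 169, which matches SAP Table 5 ("Day 169- 42 to 169 + 41 and prior to any ETP treatment"). The other eight target days in that table, from Week 13 = 85 to Week 145 = 1009, reproduce in the same way.

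**Step 2: offset.** Week 27 is 26 × 7 + 1 = Day 183. The offset from Day 1 is 182 days, and 182 / 7 = 26 weeks.

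**Step 3: weeks since first avalglucosidase alfa dose, by nominal week.**

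| Nominal week | Day 1 starters (week − 1) | Switchers (week − 27) |
|---|---|---|
| 29 | 28 | 2 |
| 37 | 36 | 10 |
| 49 | 48 | 22 |
| 73 | 72 | 46 |
| 145 | 144 | 118 |

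**Step 4: which rows mix both groups.**
- *Biochemistry* (Protocol 1.2.2 and 1.2.3): Week 28 is switchers only. Weeks 29, 33, 37, 41, 45 and 49 hold both groups. Weeks 53, 57, 65 and 69 are switchers only. The quarterly visits from Week 61 hold both.
- *Antibodies* (Protocol 9.1.1.7 and 1.2.3), if study weeks are used as labels: rows up to Week 25 hold no switchers on avalglucosidase alfa. Weeks 28, 29, 33, 41 and 45 are switchers only. Weeks 37 and 49 and later quarterly visits hold both.

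**Step 5: how many patients.** Assume the minimum sizes: 5 in the Stage 1 cohort that shares Cohort 3's dose, 5 randomised to avalglucosidase alfa in Cohort 3, and 5 controls of whom k switch. The share of switchers in that dose level is k / (10 + k). It runs from 0% (k = 0) to 5/15 = 33% (k = 5). Mean time on drug in the Week 49 row is (10 × 48 + k × 22) / (10 + k). That is 48 weeks at k = 0 and 590/15 = 39.3 weeks at k = 5. The other dose level has no switchers.

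**Step 6: is subtracting 26 weeks enough?** On an exposure clock, switcher Weeks 28, 29, 33, 37, 41, 45, 49, 61 and 73 become Weeks 2, 3, 7, 11, 15, 19, 23, 35 and 47. Only Week 2 (the Day 8 visit) coincides with a visit of the Day 1 starters. Week 3 is 1 week from Day 8 and 2 weeks from Week 5. The others are 2 weeks from the nearest laboratory or antibody visit. Protocol 10.1.2 allows ±7 days for infusions and safety assessments, and ±14 days only for other assessments. Laboratory and antibody samples are listed as safety assessments, so a 14-day relabelling falls outside the protocol window.

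**The case against.** The strongest reply is that the plan already shows the switchers cleanly elsewhere. Their ETP safety results get separate tables, ALGLU/AVAL is its own ETP group, by-cohort tables exist, and titres are listed for every patient, which is a real safeguard with about five switchers. The analysis is descriptive with no testing. It can also be argued that switchers may not enter the dose-level tables at all: SAP 2.4.3.1, for example, leaves Cohort 3 alglucosidase alfa patients out of the overall exposure duration.

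Much of this stands and limits the point. It does not remove it. The sentence on separate tables concerns ETP, while the overall group in SAP 2.4.4 names the switchers explicitly. The reset baseline does not help with the row label either. If it is used in the overall tables, a Week 49 change from baseline averages changes over about 48 weeks with changes over about 22.

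A reader might go further and infer that the antibody time courses are governed by the nominal-visit rule. The documents do not say that. The rule names laboratory, ECG and vital signs. Titres are by study visit, and the axis of the titre graphs is undefined. The misalignment is likely there, since the SAP offers no other clock, but it is an inference. A reader might also infer that ECG and vital-sign tables are affected. In SAP 2.4.4.4 and 2.4.4.5, the repeat for the overall period follows the PCSA analyses, which do not use visit labels.

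**Conclusion.** The point holds for the overall-period by-visit laboratory tables. Followed as written, the plan puts values and changes from baseline that are 26 weeks apart in exposure into the same rows from Week 29 on, in the dose level shared with Cohort 3. The offset is exact on the planned schedule. The number of patients is not: 0 to 5 of up to 15 in that dose level, assuming minimum cohort sizes and depending on how many controls switch. For antibody titre tables and graphs the same result is probable but not stated.

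It would be wrong to conclude that the safety time courses in general are in error. PAP tables, by-cohort and by-arm tables, separate switcher ETP tables, incidence, peak titre, worst-value and PCSA summaries do not depend on this label or do not pool across it. The defect is a misaligned time axis in one set of pooled displays.

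**What to change.** In SAP 2.5.3 and 2.5.4, state that overall-period by-visit laboratory and ADA tables and graphs use time since the first avalglucosidase alfa infusion, and add a table of analysis windows on that exposure scale. Do not use a fixed relabelling of switcher visits. Moving Week 29 to Week 5, for example, would label a sample taken 2 weeks after the first dose as one taken 4 weeks after it, although it lies nearer to Day 8. The alternative is to show switchers separately by visit in these displays. Keep nominal weeks for the PAP and by-cohort ETP tables.

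The cost is SAP wording and some derived variables, with no new data. The downside is that the exposure-time windows must be wider than the protocol's ±7 days to take in the switchers' schedule, which should be footnoted.

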2.5.5 Unscheduled visits

Unscheduled visit measurements of laboratory data, vital signs, and ECG will not be included in the by-visit summaries, but will be used for computation of baseline, worst values, and summary of PCSAs.

2.5.6 Pooling of centers for statistical analyses

Not planned.

2.5.7 Statistical technical issues

None.

3 INTERIM ANALYSIS

While all patients will be followed for up to 3 years during the study, the primary analysis for the study will be performed when all Cohort 3 patients have completed the 6-month PAP or discontinued from the study before completing PAP. In addition, safety analyses will be performed in multiple time points by the DMC to determine the dose for next cohort and the MTD. The DMC procedures are detailed in the DMC charter. Furthermore, an additional analysis might be performed for alglucosidase alfa submission.

Since there is only one hypothesis test for the composite score to be performed at the end of the primary analysis period, no adjustment is needed for the interim analyses. Additional analyses after PAP will be considered for supportive purpose.

4 DATABASE LOCK

The DBL for the primary efficacy analyses is planned to be approximately 30 days after last patient last visit in PAP.

The final database lock for the study is planned to be approximately 30 days after the last patient last visit in ETP.

